7.1.2.1 Special Guidelines Related to Capecitabine Toxicity

7.1.2.1.1 Diarrhea

Capecitabine can cause diarrhea, and should be **stopped at diarrhea grade ≥ 2** , and treated symptomatically (recommend IV hydration and use of loperamide for diarrhea, observing loperamide dosage recommendation and treatment start, see below). If control takes longer than 2 days, medical evaluation including relevant diagnostic procedures, alternative treatment and possible investigation of Dihydropyrimidine Dehydrogenase Deficiency (DPD) deficiency should be considered.

Capecitabine cannot be re-started until diarrhea has resolved to baseline or grade < 2.

The recommended dosage regimen for loperamide: 4 mg at the first onset of late diarrhea and then 2 mg every 2 hours until the patient is diarrhea-free for at least 12 hours. During the night, the patient may take 4 mg of loperamide every 4 hours. Note: This dosage regimen exceeds the usual dosage recommendations for loperamide. Premedication with loperamide is not recommended.

The use of drugs with laxative properties should be avoided because of the potential for exacerbation of diarrhea. Patients should be advised to contact their physician to discuss any laxative use.

Patients with \geq grade 3 diarrhea should also be evaluated for *C. difficile*.

Patients with neutropenia and diarrhea should be considered for empiric use of prophylactic antibiotics, such as oral quinolones.

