6.4.2 Administration

At the discretion of the treating physician, the patient may receive 850mg/m² or 1000mg/m² of capecitabine. Capecitabine will be administered at a dose of 850/1000 mg/m² twice daily, for a total daily dose of 1700/2000 mg/m² beginning the morning of Day 1 of each 3-week cycle and continuing through the evening of Day 14; except in the "biomarker cycle" (i.e. first cycle for subjects in the dose expansion cohort). During the biomarker cycle, capecitabine will begin on Day 8 (to allow for one week of pembrolizumab monotherapy for biomarkers). A treatment window of +/- 3 days of day 1 is allowed for cycle 2 and all subsequent cycles.

See current capecitabine package insert for dosing instructions in patients with moderate renal impairment.

The dose of capecitabine will be calculated on the basis of milligrams of drug per square meter (mg/m²) of body surface area (BSA). The dose of capecitabine will be rounded to the nearest dose that can be obtained by using the 500 mg tablets. Since capecitabine tablets cannot be split, patients may take different numbers of pills in the morning and evening in order to achieve the appropriate dose. The following is an example of how dose rounding may be performed:

Explanation: $[\{BSA\} m^2 \times \{dose level\} mg/m^2] \times 2 = \text{Daily Dose mg}$
Daily Dose mg $\div 500$ mg tablet = number of tablets per day, rounded to whole tablets
Divide number of whole tablets per day into 2 doses for morning (AM) and evening (PM)

Calculation: $[1.68m^2 \times 1000mg/m^2] \times 2 = 3360mg$
 $3360mg \div 500mg$ tablet = 6.72 tablets per day, rounded to 7 tablets per day
Divide 7 tablets into 2 doses = three 500mg tablets in AM and four 500mg tablets in PM

The dose will be recalculated per institutional standard (e.g., based on the new body surface area prior to the start of each cycle only if the weight changes by 10% from baseline).

Capecitabine will be taken orally. The total daily dose should be taken as two divided doses approximately 12 hours apart, within 30 minutes after the ingestion of food, ideally after breakfast and the evening meal. Tablets should be swallowed with approximately 200 ml of water (not fruit juices). Tablets are not scored and should not be split. If needed, capecitabine may be dissolved for administration either orally or via G or J tube but patient must receive safety handling training from pharmacy personnel.

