7.1 Dose Modifications

Subjects experiencing one or more AEs due to the study drug(s) may require dose modification(s) as described in [Section 7.1.1](#) and [Section 7.1.2](#). At the discretion of the Investigator, dose modifications are permitted outside of the those provided in the protocol if the Investigator feels it is in the interest of the subject's safety (e.g., due to multiple toxicities, persistent toxicities, intercurrent illness, or short term compliance or monitoring issues, etc.).

Subjects may need to be followed at least weekly when any study drug is held for toxicity until the toxicity returns to Grade ≤ 1 or is determined to be chronic or irreversible.

Dosing interruptions are permitted in the case of medical / surgical events or logistical reasons not related to study therapy (e.g., elective surgery, unrelated medical events, patient vacation, and/or holidays). Subjects should be placed back on study therapy within 4 weeks of the scheduled interruption, unless otherwise discussed with the Lead PI. The reason for interruption should be documented in the patient's study record. Dosing may be interrupted if there is a need for local palliative radiation therapy, with the approval of the lead PI. In this case, protocol-based therapy cannot be resumed until patients are at least 14 days out from the end of radiation.

If pembrolizumab is permanently discontinued, the subject will be discontinued from study treatment. Maximum duration of treatment for pembrolizumab will be up to 35 cycles. If patients discontinue oxaliplatin due to intolerance, they can be maintained on capecitabine and pembrolizumab. If capecitabine is not tolerated, pembrolizumab monotherapy may be continued. Re-introduction of oxaliplatin is permitted provided neuropathy has improved.

All dose modifications and reasons for modification must be recorded in the CRF.

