7.1.2 XELOX Dose Modifications

Toxicity Grade ^a	Occurrence	Oxaliplatin	Capecitabine
DIARRHEA			
Grade 1	Any	Maintain dose	Maintain dose

Grade 2	Any	If tolerable: Maintain dose If intolerable: Hold until grade ≤ 1 , then resume at 80% of current dose	If tolerable: Maintain dose If intolerable: Hold until grade ≤ 1 , then resume at 80% of current dose ^b
Grade 3	1 st – 3 rd	Hold until grade ≤ 1 , then resume at 80% of current dose	Hold until grade ≤ 1 , then resume at 80% of current dose
	4 th and higher	Hold until grade ≤ 1 , –obtain permission of PI to resume at 80% of current dose	Hold until grade ≤ 1 , obtain permission of PI to resume at 80% of current dose–
Grade 4	1 st	Hold until grade ≤ 1 , then resume at 60% of current dose	Hold until grade ≤ 1 , then resume at 60% of current dose
	2 nd and higher	Hold until grade ≤ 1 , obtain permission of PI to resume at 60% of current dose ^b	Hold until grade ≤ 1 , obtain permission of PI to resume at 60% of current dose ^b

VOMITING			
Grade 1	Any	Maintain dose	Maintain dose
Grade 2	Any	Maintain dose	Maintain dose
Grade 3 [occurring within 3 days of Oxaliplatin dosing despite optimal anti-emetic prophylaxis]	1 st	Hold until grade ≤ 1 , then resume at 80% of current dose ^c	Maintain dose
	2 nd and higher	Hold until grade ≤ 1 , then resume at current dose. ^c	Maintain dose
Grade 4 (TPN, intensive care or hemodynamic collapse) [occurring within 3 days of Oxaliplatin dosing despite optimal anti-emetic prophylaxis]	1 st	Hold until grade ≤ 1 ^c , then resume at 60% of current dose	Hold until grade ≤ 1 , then resume at 60% of current dose
	2 nd and higher	Discontinue	Hold until grade ≤ 1 , obtain permission of PI to resume at 60% of current dose

a. National Cancer Institute Common Terminology Criteria Version 3.
 b. Continue treatment if it is considered to be in the best interest of the patient
 c. **NOTE:** After Cycle 1, at the discretion of the treating physician, once there is recovery of the toxicity to grade ≤ 1 , the treating physician may choose, to hold oxaliplatin and continue capecitabine and pembrolizumab at current dose as clinically indicated. If the treating physician chooses to restart oxaliplatin later in the patient's treatment course, the dose of oxaliplatin at which the patient restarts should be one dose level lower than last dose level on which patient was treated. The specific treatment approach used and dose modifications that occur are required to be reported in the Case Report Forms.

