Grade 2	Any	Maintain dose	Maintain dose
Grade 3($\geq 0.5 - < 1 \times 10^9 /L$)	1 st	Hold until grade ≤ 1 , then resume at current dose	Maintain dose
	2 nd and higher	Hold until grade ≤ 1 , then resume at 80% of current dose ^d	Maintain dose
Grade 4 ($< 0.5 \times 10^9 /L$)	1 st	Hold until grade ≤ 1 , then resume at 80% of current dose ^{b,c,d}	Hold until grade ≤ 1 , then resume at 80% of the current dose ^{b,c}
	2 nd and higher	Hold until grade ≤ 1 , obtain permission of PI to resume at 60% of current dose ^d	Hold until grade ≤ 1 , obtain permission of PI to resume at 60% of current dose
FEBRILE NEUTROGENIA			
Grade 3 (neutropenia and fever $\geq 38.5C$)	1 st – 2 nd	Hold until resolution of fever and neutropenia to grade ≤ 1 , then resume at 60% of current dose ^d	Hold until resolution of fever and neutropenia to grade ≤ 1 , then resume at 60% of current dose ^{b,c,d}
	3 rd	Discontinue Protocol Therapy	Discontinue Protocol Therapy
Grade 4 (neutropenia and fever $> 38.5 C$)	Any	Discontinue Protocol Therapy	Discontinue Protocol Therapy
THROMBOCYTOPENIA			
Grade 1 ($< LLN - < 75.0 \times 10^9 /L$)	Any	Maintain dose	Maintain dose
Grade 2($\geq 50.0 - < 75.0 \times 10^9 /L$)	1 st	Hold until grade ≤ 1 , then resume at 80% of current dose ^d	Maintain dose
	2 nd and higher	If stable grade 2, maintain current dose	Maintain dose
Grade 3($\geq 25.0 - < 50.0 \times 10^9 /L$)	1st	Hold until grade ≤ 1 , then resume at 80% current dose ^d	Hold until grade ≤ 1 , then resume at 80% of the current dose
	2nd and higher	Hold until grade ≤ 1 , then resume at 80% current dose ^d	Hold until grade ≤ 1 , then resume at 80% of the current dose ^b
Grade 4($< 25.0 \times 10^9 /L$)	1st	Hold until grade ≤ 1 , then resume at 60% of the current dose ^{b,d}	Hold until grade ≤ 1 , then resume at 60% of the current dose ^b
	2nd	Discontinue Protocol Therapy	Discontinue Protocol Therapy

HEMOGLOBIN			
Grade 1 < LLN - 10.0 g/dL < LLN - 100 g/L < LLN - 6.2mmol/L	Any	Maintain dose	Maintain dose ^b
Grade 2 8.0 - < 10.0 g/dL 80 - < 100 g/L 4.9 - < 6.2 mmol/L	Any	Maintain dose	Maintain dose
Grade 3 6.5 - < 8.0 g/dL 65 - < 80 g/L 4.0 - < 4.9 mmol/L	Any	Maintain dose	Maintain dose
Grade 4 < 6.5 g/dL < 65 g/L < 4.0 mmol/L	Any	Hold until \leq grade 2; then resume at current dose, may transfuse ^b	Maintain dose ^b
OTHER HEMATOLOGIC TOXICITY			
Grades 1 - 4	Any	Maintain dose	Maintain dose

- a. National Cancer Institute Common Terminology Criteria Version 3.0

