10.1 Adverse Events

An adverse event (AE) is defined as any untoward medical occurrence in a patient or clinical investigation subject administered a pharmaceutical product and which does not necessarily have to have a causal relationship with this treatment. An adverse event can therefore be any unfavorable and unintended sign (including an abnormal laboratory finding, for example), symptom, or disease

temporally associated with the use of a medicinal product or protocol-specified procedure, whether or not considered related to the medicinal product or protocol-specified procedure. Any worsening (i.e., any clinically significant adverse change in frequency and/or intensity) of a preexisting condition that is temporally associated with the use of the supporting company product(s), is also an AE.

Changes resulting from normal growth and development that do not vary significantly in frequency or severity from expected levels are not to be considered AEs. Examples of this may include, but are not limited to, teething, typical crying in infants and children and onset of menses or menopause occurring at a physiologically appropriate time.

Supporting company product includes any pharmaceutical product, biological product, device, diagnostic agent or protocol-specified procedure, whether investigational (including placebo or active comparator medication) or marketed, manufactured by, licensed by, provided by or distributed by the supporting company for human use.

AEs may occur during the course of the use of supporting company product(s) in clinical trials or within the follow-up period specified by the protocol, or prescribed in clinical practice, from overdose (whether accidental or intentional), from abuse and from withdrawal.

Progression of the cancer under study is not considered an AE unless it is considered to be drug related by the Investigator.

AEs will be documented from the date of first dose of study drug through 30 days after the last dose of study drug. All Grade 2-5 AEs as well as special reporting circumstances, such as exposure via a parent during pregnancy or breast-feeding, overdose, medication error, misuse, abuse, off-label use or occupational exposure must be recorded on the CRF.

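### For tolerable grade 2 diarrhea, the Section 7.1.2 table maintains capecitabine while Section 7.1.2.1.1 stops it, and no text says which rule governs

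*Combined protocol and SAP*

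**What the plan says.** Section 7.1.2 (XELOX Dose Modifications) has a diarrhea table with separate oxaliplatin and capecitabine columns. For grade 2, at any occurrence, the capecitabine cell begins "If tolerable: Maintain dose". If the diarrhea is intolerable, the cell requires a hold until grade 1 or lower and then 80% of the current dose.

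Section 7.1.2.1.1, among the special guidelines on capecitabine toxicity, says in bold that the drug should be "stopped at diarrhea grade" 2 or higher. The restart rule follows: "Capecitabine cannot be re-started until diarrhea has resolved to baseline or grade" below 2. Neither sentence separates tolerable from intolerable diarrhea.

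Section 7.1 adds a general permission: "At the discretion of the Investigator, dose modifications are permitted outside of the those provided in the protocol", where the investigator judges this to be in the interest of the patient's safety. It also requires a record: "All dose modifications and reasons for modification must be recorded in the CRF".

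**The concern.** A patient with tolerable grade 2 diarrhea is told by one text to keep taking capecitabine and by the other to stop. This is a safety instruction. Under Section 3.1 the dose expansion cohort, 30 of the 35 planned evaluable patients, may be enrolled at external institutions as well as the lead site, so practice can split by site.

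Two things are at stake. The first is consistent handling of a toxicity that Section 1.2.3 lists among the most common capecitabine reactions and describes as sometimes severe. The second is the description of tolerability, a secondary objective in Section 2.2, because capecitabine interruptions would partly reflect which text a site followed. Section 11.3 also requires deviations to be documented and reported, and here it is unclear which action would be the deviation.

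**Working it through.** No figure in the plan bears on this point, so the check is a side-by-side reading of the capecitabine column of the diarrhea table (Section 7.1.2) against Section 7.1.2.1.1.

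| Branch in the table | Table | Section 7.1.2.1.1 | Agree on whether to hold? |
|---|---|---|---|
| Grade 1 | maintain | not triggered | yes |
| Grade 2, tolerable | maintain | stop | **no** |
| Grade 2, intolerable | hold | stop | yes |
| Grade 3, 1st to 3rd | hold | stop | yes |
| Grade 3, 4th and higher | hold | stop | yes |
| Grade 4, 1st | hold | stop | yes |
| Grade 4, 2nd and higher | hold | stop | yes |

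One branch of seven conflicts. In the branches that hold, the restart thresholds also match, since a grade below 2 is the same as grade 1 or lower. Section 7.1.2.1.1 merely adds return to baseline as an alternative.

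The next step is to look for text that settles the conflict.

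- **Could maintaining the dose mean holding and then resuming at the same level?** No. The same cell sets it against a hold for intolerable diarrhea. Where the protocol wants a hold without a reduction it says so, as for oxaliplatin at a first grade 3 neutropenia in the same section.
- **Does the heading of the special guidelines give them priority?** It does not say so. The hand-foot and stomatitis subsections refer the reader to a dose table. The diarrhea subsection has no such link.
- **Does investigator discretion in Section 7.1 settle it?** It permits departures for safety but does not say which rule is the default.
- **Does footnote b of the table settle it?** It allows treatment to continue in the patient's best interest. It does not mention Section 7.1.2.1.1, and it is not attached to the tolerable branch.
- **Is the instruction to stop only advisory?** The stop sentence is phrased as a recommendation, but the restart sentence is a prohibition.

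The last step is to see what does not depend on the conflict. The diarrhea criterion in the DLT definition (Section 3.2.1) starts at grade 3. The primary PFS analysis in Section 9.1.1 follows patients for progression even after removal from treatment for toxicity, and a temporary capecitabine hold is not a removal. The power statement uses no dosing information.

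**The case against.** The best defence is that a specific, bold guideline placed after a general table in the same section is naturally read as qualifying it. A site that stops capecitabine for safety is also covered by the discretion in Section 7.1. Together these favour the cautious rule. That is a sensible reading and it supports the direction of the fix, but it is an inference. A site that continues the drug is doing exactly what the table says.

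A second defence is that the scopes differ: Section 7.1.2.1.1 concerns diarrhea caused by capecitabine, while the table covers diarrhea on the whole regimen. The instruction to stop carries no attribution condition, however. Even if it did, the table would still apply to capecitabine-related diarrhea, so the two would still overlap.

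A third is that the effect is small: one branch, a temporary interruption, and variation that the CRF would show. This stands, and it limits the weight of the point. It does not make the two instructions compatible.

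It is also fair to say that the forward benefit is uncertain. This is version 9.0, dated March 2022, of a protocol first issued in 2017, and the documents do not say how many patients remain on treatment.

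**Conclusion.** The contradiction is real and unresolved, and the plan cannot be followed as written for tolerable grade 2 diarrhea. It should be corrected because it is a dosing rule for patient safety and the correction is cheap. Its scope is one of seven capecitabine branches. That measures how far the conflict reaches in the text, not how often it arises.

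Three stronger readings are tempting, and the documents do not support them.

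- A reader might infer a definite loss of capecitabine dose. The documents give neither the length of such holds nor the rate of tolerable grade 2 diarrhea on this regimen. A hold falling in the off-drug week could cost no doses at all.
- A reader might infer harm to the efficacy result. The PFS definition and primary analysis, the DLT rule and the design figures do not change with this choice.
- A reader might extend the point to other parts of Section 7, such as the febrile neutropenia rows or the two CTCAE versions cited. The febrile neutropenia rows carry different grade labels, with neutrophil limits by grade printed just above them. The documents show no consequence of the version difference, and establishing one would need the grading texts themselves.

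**What to change.** In the grade 2 capecitabine cell of the Section 7.1.2 diarrhea table, replace the tolerable branch with: *hold until baseline or grade ≤1, then resume at current dose*. Keep the intolerable branch at 80% on resumption, as now. Leave the oxaliplatin cell unchanged, because Section 7.1.2.1.1 concerns capecitabine only.

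The clinical team must confirm the resume dose: resuming at the current dose merges the two rules, and neither states it outright. If the team instead prefers to continue the drug, limiting Section 7.1.2.1.1 to intolerable grade 2 and above, or stating which text governs, would also remove the conflict.

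For patients already treated, list every grade 2 diarrhea event and whether capecitabine was held. Listing all of them avoids reconstructing which were judged tolerable. The data should already exist: Section 10.1 requires CRF entry of "All Grade 2-5 AEs as well as special reporting circumstances", and Section 7.1 requires every dose modification with its reason.

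The cost is a short amendment with IRB/IEC approval under Section 11.2, and some temporary capecitabine interruptions that the table would not have required. Sample size, visits and data collection do not change.

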7.1.2.1.2 Hand-Foot Syndrome

Toxicity Grade ^a	Occurrence	Oxaliplatin	Capecitabine
1	Any	Maintain dose	Maintain dose
2	1 st – 3 rd	Maintain dose	Hold until grade ≤1, then resume 80% of current dose
	4 th and higher	Discontinue Protocol Therapy	Discontinue Protocol Therapy
3	1 st – 2 nd	Maintain dose	Hold until grade ≤1, then resume at 80% of current dose
	3 rd and higher	Discontinue Protocol Therapy	Discontinue Protocol Therapy

- a. National Cancer Institute Common Terminology Criteria Version 3.0
- b. Continued treatment only if it is considered to be in the best interest of the patient
- c. **NOTE:** After Cycle 1, at the discretion of the treating physician, once there is recovery of the toxicity to grade ≤1, the treating physician may choose, to hold oxaliplatin and continue capecitabine and pembrolizumab at current dose as clinically indicated. If the treating physician chooses to restart oxaliplatin later in the patient's treatment course, the dose of oxaliplatin at which the patient restarts should be one dose level lower than last dose level on which patient was treated. The specific treatment approach used and dose modifications that occur are required to be reported in the Case Report Forms.

*Applies only for grading hand–foot syndrome and should not be used to describe any other skin event and/or other cutaneous area.

In the case of a discrepancy between the clinical domain and the functional domain, the assigned grade should correspond to the domain with the higher grade.

Grade 2-3 Hand-Foot Skin Reaction

Treat symptomatically (recommended use of emollients) and according to above table. The use of vitamin B6 (Pyridoxine) has been reported to be of possible benefit for symptomatic or secondary prophylactic treatment, but due to a possible interaction with cisplatin (and thus possibly oxaliplatin) the use of B6 is not permitted in this trial.

7.1.2.1.3 Stomatitis/Oral Mucositis/Mouth Ulcers

Stomatitis/oral mucositis/mouth ulcers due to capecitabine should be treated using local supportive care. Please follow the paradigm below for treatment of stomatitis/oral mucositis/mouth ulcers:

- For mild toxicity (grade 1), use conservative measures such as non-alcoholic mouth wash or salt water (0.9%) mouth wash several times a day until resolution.
- For more severe toxicity (grade 2 in which case patients have pain but are able to maintain adequate oral alimentation, or grade 3 in which case patients cannot maintain adequate oral alimentation), the suggested treatments are topical analgesic mouth treatments (i.e., local anesthetics such as, benzocaine, butyl aminobenzoate, tetracaine hydrochloride, menthol, or phenol) with or without topical corticosteroids, such as triamcinolone oral paste 0.1% (Kenalog in Orabase®). For patients with grade 2 and above stomatitis, capecitabine may be held or dose reduced according to dose reduction table for non-hematologic toxicities (Section 3.3.4).

- Agents containing hydrogen peroxide, iodine, and thyme derivatives may tend to worsen mouth ulcers. It is preferable to avoid these agents. The ingredient list of used toothpastes and mouthwashes should be checked for these agents.
- Antifungal agents must be avoided unless a fungal infection is diagnosed. Topical antifungal agents are preferred if an infection is diagnosed. Similarly, antiviral agents such as acyclovir should be avoided unless a viral infection is diagnosed.

Note: Stomatitis/oral mucositis should be appropriately graded using the functional grading given on the NCI-CTC for Adverse Events, version 3.0.

